4.3 EXCLUSION CRITERIA

- 1. Recent (i.e., within three (3) months prior to Screening) evidence or medical history of unstable concurrent disease such as: documented evidence or history of clinically significant hematological, endocrine, pulmonary, gastrointestinal, cardiovascular, hepatic, psychiatric, immunological, or clinically significant neurological disease.
- 2. No history of T2DM
- 3. BMI of less 24 and greater 40 kg/m2
- 4. Unstable body weight (change of greater than ±3-4lbs over the preceding 3 months
- 5. Subjects not currently receiving exenatide or liraglutide
- 6. Subjects participating in an excessively heavy exercise program
- 7. Subject with a feeding/sleeping schedule different from a daytime feeding/night time sleeping schedule
- 8. Subjects taking medications known to alter glucose metabolism (with the exception of any combination of metformin,pioglitazone, sulfonylureas, and insulin) or which affect brain neurosynaptic function are excluded.
- 9. Subjects with evidence of major organ system disease as determined by physical exam, history, and screening laboratory data
- 10. Pregnant subjects or subjects unwilling to use birth control during their study enrollment
- 11. Blood donation of approximately 1 pint (500 mL) within 8 weeks prior to Screening 12. Subjects that are allergic to bromocriptine or any of the other ingredients in Cycloset, or take ergot medicines, breastfeeding or have history of syncope or Type 1 diabetes mellitus0
- 12. Other severe acute or chronic medical or psychiatric condition or laboratory abnormality that may increase the risk associated with study participation or investigational product administration or may interfere with the interpretation of study results that, in the judgment of the investigator, would make the subject inappropriate for entry into this study subjects of reproductive potential

Female subjects must not become pregnant during the study. Absence of pregnancy must be checked by serum pregnancy testing at the screening visit (Visit 0).

Female subjects of childbearing potential must use a medically accepted contraceptive regimen. If a female subject becomes pregnant during the trial, she must be withdrawn and followed up until the outcome of the pregnancy is known. If pregnancy occurs, the investigator must contact the sponsor immediately for further instruction. Both the detection and the outcome of the pregnancy must be reported to the sponsor on special forms ("Drug Exposure Via Parent – Data Collection Form"), which will be provided to the investigator as needed.

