Subjects will be rested in the supine position for 15 minutes. Measurements for the assessment of aortic pulse wave velocity (PWV) will then be taken immediately after measurement of brachial blood pressure. PWV is determined by simultaneous measurement of arterial pressure waves at the carotid and femoral arteries with sensitive pressure transducers place on the skin overlying the carotid and femoral arteries. This is a completely noninvasive procedure using previously described and published techniques (Circulation 2006; 113: 1213-1225). The surface distance from suprasternal notch to the distal (femoral) recording site is measured, and the pressure wave transit time is calculated using a foot-of-the-wave to foot- of-the-wave method. PWV is calculated by dividing the distance to the distal site by the pressure wave transit time. Data are collected by a single trained observer, and the mean of at least 2 PWV measurements is taken for each subject.

Meal Tolerance Test (MMT)

Following a 10-12 hour overnight fast, catheters will be placed in the antecubital vein or hand vein, one for infusion of tritiated glucose and one for blood withdrawal. At -180 minutes baseline blood samples (see attached flow sheet) will be obtained and a prime (40 uCi x FPG/100) – continuous (0.40 uCi/min) will be started. Blood samples for determination of plasma, glucose, insulin, C-peptide, glucagon, FFA, glucagon-like peptide-1, and glucose-dependent insulinotropic polypeptide and tritiated glucose and 14C-glucose radioactivity will be obtained at -180, -30, -20, -10, and 0 minutes. At time zero subjects will ingest a mixed meal (75 grams of glucose, 25 grams of fat, 20 grams of protein, 600 kcal) over 15-20 minutes. The glucose will be labeled with

100 uCi of 1-14C-glucose. Plasma samples for substrates, hormones, and radioactivity will be obtained every 15 minutes for 5 hours. Plasma samples for catecholamines (CA) will be collected at -10, 0, 60, 120, and 240 minutes.

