4.2 INCLUSION CRITERIA

- 1. Type 2 diabetes male or female subjects between the ages of 30 and 70 years of age, inclusive, at Screening
- 2. BMI = 24-40 kg/m2
- 3. HbA1c = 7.5-10.0%
- 4. Stable body weight (±3-4lbs) over the preceding 3 months
- Subjects currently receiving a stable dose of exenatide (2mg/week) or liraglutide (1.2-1.8 mg/day) for at least 90 days prior to determination of baseline A1C and eligibility for enrollment in the study protocol.
- 6. Subjects with a daytime feeding/night time sleeping schedule
- 7. Subjects with no evidence of major organ system disease as determined by physical exam, history, and screening laboratory data
- 8. Women must be of non-childbearing potential as defined by one of the following:
 - a. Women >45 and < 60 years of age at Screening, who have been amenorrheic for at least 2 years
 - b. Women who have had a documented hysterectomy and/or bilateral oophorectomy
 - c. Women > 60 years of age
- 9. Females of childbearing potential with a negative pregnancy test at Screening and using one of the following forms of contraception for the duration of participation in the study (i.e., until Follow-up 7-14 days post last dose):
 - a. Oral contraceptive
 - b. Injectable progesterone
 - c. Subdermal implant
 - d. Spermicidal foam/gel/film/cream/suppository
 - e. Diaphragm with spermicide
 - f. Copper or hormonal containing IUD
 - g. Sterile male partner vasectomized > 6 month pre-dosing.
- 10. Evidence of a personally signed and dated informed consent document indicating that the subject has been informed of all pertinent aspects of the study
- 11. Subjects must be willing and able to comply with scheduled visits, treatment, laboratory tests and study procedures.

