7.2 DESCRIPTION OF STUDY DAYS

7.2.1 Screening - Visit 0

Screening of subjects will occur at Visit 0.

- Consent form will be signed
- · Each subject will be assigned a study subject number
- Assessment of inclusion/exclusion criteria will be performed
- Medical history, including demographic and background assessments will be documented in the CRF
- Routine physical examination will be performed
- ECG test will be performed
- Blood will be taken for the determination of HbA1c, FPG, lipids, clinical chemistry variables (and serum pregnancy test for women of child-bearing potential); and hematology (see study schedule). Total amount of blood drawn at this visit will be approximately 20 ml.

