7.2.2.2 Baseline - Visit 2 (Visit 1 + 7-10 days)

- Subjects will arrive in the morning after an overnight fast (defined as no caloric intake for 10-12 hours)
- Study entry criteria will be reviewed
- All adverse events (including serious adverse events), hypoglycemia and concomitant medications since the last visit will be documented
- Subject will be weighed.
- Postural blood pressure measurements will be obtained first with the subject lying down and then repeated after 5 minutes of standing.
- Endo-PAT will be performed t0 and t90 of meal tolerance test
- 5-hour Mixed Meal Tolerance test (MMT) will be conducted.
- Blood samples will be drawn at various time points as detailed in the Study Design section and Study Schedule table above. Total amount of blood drawn at this visit will be approximately 350 ml.
- Ambulatory Blood Pressure Monitoring (ABPM) device will be set up
- 24 hour urine collection instructions will be given

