7.2.2.3 Baseline – Visit 3 (Visit 2 + 3-5 days)

- ABPM device will be returned and data downloaded.
- 24 hour urine collection will be returned
- DXA for body composition will be conducted
- Bloods for inflammatory markers and white blood cell isolation. Total amount of blood drawn at this visit will be approximately 20 ml.
- First dose of Cycloset will be administered in the CRC with a one hour post dose observation period
- Instructions for titration of Cycloset will be reviewed.

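### The only pregnancy test is at screening, two to five weeks before the first tracer, DXA scan and dose, and none is repeated before the month 4 tracer study

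*Combined protocol and SAP*

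**What the plan says.** **Who may enrol.** Section 4.2, inclusion 8 reads "Women must be of non-childbearing potential as defined by one of the following". Inclusion 9 then admits "Females of childbearing potential with a negative pregnancy test at Screening", provided that they use one of the listed contraceptive methods. Section 4.3 also requires contraception in women of childbearing potential, and section 9.1 has a withdrawal rule for those who stop it in order to conceive.

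**When pregnancy is tested.** Section 4.3 states "Absence of pregnancy must be checked by serum pregnancy testing at the screening visit (Visit 0". The Visit 0 bloods in section 7.2.1 include a "serum pregnancy test for women of child-bearing potential". The visit descriptions in sections 7.2.2 and 7.2.3 name no further test, and the study schedule has no row for one.

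**What subjects are exposed to.**
- Visit 2: the meal test in section 3.1 uses two venous catheters, "one for infusion of tritiated glucose and one for blood withdrawal", and the meal contains 100 uCi of 14C-glucose.
- Visit 3: a DXA scan, and "First dose of Cycloset will be administered in the CRC with a one hour post dose observation period" (section 7.2.2.3).
- Visit 7: the tracer meal test again, with DXA at Visit 7 or Visit 8.

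**Other safeguards.** The Visit 2 list includes "Study entry criteria will be reviewed". Exclusion 10 bars pregnant subjects and those who will not use birth control. Section 4.3 adds "If a female subject becomes pregnant during the trial, she must be withdrawn", and section 8.1.3 requires immediate reporting of any pregnancy.

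**The concern.** The protocol treats pregnancy as disqualifying: it is an exclusion, a ground for mandatory withdrawal and a reportable event. Those rules work only if a pregnancy is found, and after Visit 0 no step is specified that would find an unrecognised one.

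Two kinds of pregnancy can slip through: one too early to detect at Visit 0, and one conceived afterwards. Either could meet two radioactive tracers, an X-ray scan and study drug without any protocol deviation. The tracers and the DXA scans are done for measurement and offer the subject no treatment benefit, so there is little to set against avoidable exposure.

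The conflict between inclusions 8 and 9 makes this worse, because the text does not settle which women need testing at all.

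**Working it through.** The protocol states no interval from test to exposure, so there is no figure to reproduce. The intervals follow from the visit windows.

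**Inputs**
- Visit 0 to Visit 1: 7 to 21 days (study schedule, screening at week -3 to -1).
- Visit 1 tolerance: ±3 days (section 7.2.2.1).
- Visit 1 to Visit 2: 7 to 10 days (study schedule; section 7.2.2.2).
- Visit 2 to Visit 3: 3 to 5 days (study schedule; section 7.2.2.3).
- Visit 7: month 4, ±3 days (section 7.2.3.1). Assumption: month 4 is day 112 after first dose, in line with the 16-week treatment period in the schedule and month 1 falling on day 28 (section 7.2.2.6).
- Visit 7 to Visit 8: 3 to 5 days.

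**Age of the screening test at each exposure (sum of minima to sum of maxima)**

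| Exposure | Nominal (days) | With visit tolerances (days) |
|---|---|---|
| First tracer, Visit 2 | 7+7 = 14 to 21+10 = 31 | 4+7 = 11 to 24+10 = 34 |
| First DXA and first dose, Visit 3 | 14+3 = 17 to 31+5 = 36 | 11+3 = 14 to 34+5 = 39 |
| Second tracer, Visit 7 | 17+112 = 129 to 36+112 = 148 | 14+109 = 123 to 39+115 = 154 |
| Second DXA, if at Visit 8 | 129+3 = 132 to 148+5 = 153 | 123+3 = 126 to 154+5 = 159 |

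**Sensitivity of the month 4 figure.** The protocol does not say where month 4 is counted from. Taking 112 to 122 days for four months, before the Visit 7 tolerance:
- counted from Visit 1: 7+112 = 119 to 21+122 = 143 days;
- counted from first dose: 17+112 = 129 to 36+122 = 158 days.

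On either count, the only test is about 4 to 5 months old at the second tracer study.

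**Does the Visit 2 review close the gap?** The review is of the entry criteria, and inclusion 9 asks for a negative test at screening. A site can complete the review on the Visit 0 result and be fully compliant.

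**Effect of a Visit 2 test.** The gap from test to first dose becomes the Visit 2 to Visit 3 interval: 3 to 5 days instead of 17 to 36.

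**The case against.** The strongest reply is that the exposed group may be empty. Applied as written, inclusion 8 admits no woman of childbearing potential, and the protocol gives no count of such women among the 15 subjects. But inclusion 9, the contraception rule in section 4.3, the Visit 0 test and the withdrawal rule in section 9.1 would serve no purpose on that reading, and the age range of 30 to 70 includes women who could conceive. What stands is that the number at risk is unknown.

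Second, there are other safeguards: mandatory contraception, the entry review on the day of the first tracer, and medical history at Visits 4 to 7. These give several chances to catch a known or suspected pregnancy. They do not detect an unrecognised one, and contraception does nothing about a conception shortly before Visit 0.

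Third, the upper limits are open to argument. The tolerance-based maxima imply 24 days from Visit 0 to Visit 1, which exceeds the stated screening phase of up to three weeks. The schedule header also appears to place Visits 0 to 3 under screening. If the three-week cap covered all of them, the gap to first dose would be at most 21 days. However, section 7.2.2 lists Visits 1 to 3 under the treatment period, and the explicit visit intervals allow 31 and 36 days. Even on the stricter reading the minimum of 17 days to first dose is unchanged, so the gap is still more than two weeks.

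Finally, the protocol gives no fetal dose or hazard estimate, and none is claimed here. The point concerns subject safety and affects no endpoint or analysis.

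**Conclusion.** The concern holds. The protocol specifies one pregnancy test, at screening, and none before any of the later exposures. Nominally that test is 14-31 days old at the first tracer and 17-36 days old at the first DXA scan and first dose. At the second tracer study it is about 4 to 5 months old (129-148 days if month 4 is day 112 after first dose). The first two ranges come directly from the schedule; the last depends on how month 4 is counted.

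The conclusion assumes that women of childbearing potential may enrol, as inclusion 9 and sections 4.3, 7.2.1 and 9.1 provide. The number affected and the size of any fetal risk cannot be derived from the protocol. This is a safety gap that should be closed, and closing it does not alter the design.

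**What to change.** - Visit 2: test women of childbearing potential, with the result known before the tracer starts at -180 minutes. A spot urine test, or blood drawn before the infusion, is enough.
- Visit 7: repeat the test, with the result known before the meal test and DXA.
- Visit 3: a rapid test before DXA and the first dose is a reasonable addition. It is less pressing once Visit 2 is covered.
- Section 4.2: reword inclusions 8 and 9 so that a woman must meet one or the other. This makes clear who is tested.
- Study schedule: add a pregnancy-test row that matches the visit text.

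The cost is two or three visit bullets, a schedule row, a short rewording of inclusions 8 and 9, and one simple test per visit in a subset of 15 subjects. The drawbacks are a short wait for the result before the infusion, and a urine or early blood sample at Visits 2 and 7 that is not now scheduled. Visit timing, endpoints and sample size stay as they are.

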5 STUDY TREATMENTS

5.1 DETAILS OF STUDY TREATMENTS

All subjects will receive Cycloset, 0.8 mg/day, with the dose increased by 0.8 mg/day every week to a maximum of 3.2 mg/day, or as tolerated to a minimum dose of 2.4 mg/day, added on to usual diabetes therapy consisting of a stable dose for at least 90 days of exenatide (2mg/week) or liraglutide (1.2-1.8 mg/day). Subjects must be on either exenatide or liraglutide as part of their standard care to be eligible for study participation. Subjects will maintain their maximum tolerated dose of Cycloset for the duration of the study.

5.2 SUPPLIES AND ACCOUNTABILITY

Cycloset tablets will be provided by the Sponsor. Accountability will be performed at the study site at the end of each subject's treatment period.

5.3 COMPLIANCE

Subjects will be instructed to bring their current, used and unused (vials) of study drug to every visit.

5.4 RUN-IN MEDICATION

There is no run-in period prior to enrollment. Subjects will remain on their current regimen of either exenatide or liraglutide. No medications known to alter glucose metabolism (with the exception of metformin and/or pioglitazone),or which effect brain neurosynaptic function are allowed.

6 PRIOR AND CONCOMITANT ILLNESSES AND TREATMENTS

6.1 PRIOR AND CONCOMITANT ILLNESSES

Additional illnesses present at the time informed consent is given are regarded as concomitant illnesses and must be documented in the case report form. Relevant past illnesses must also be documented in the case report form.

Illnesses first occurring or detected during the study, and worsening of a concomitant illness during the study, are to be regarded as adverse events and must be documented as such in the case report form.

6.2 PRIOR AND CONCOMITANT TREATMENTS

All treatments being taken by the subjects on entry to the study or at any time during the study in addition to the study drug are regarded as concomitant treatments and must be documented on the appropriate pages of the case report form.

Concomitant medications should be kept to a minimum during the study and adhere to the inclusion/exclusion criteria described above. However, if these are considered necessary for the subject's welfare and are unlikely to interfere with the investigational products, they may be given at the discretion of the investigator and recorded in the case report form.

Subjects on systemic corticosteroids will be excluded.

7 OVERVIEW OF DATA COLLECTION AND STUDY PROCEDURES

7.1 STUDY PROCEDURES AND SCHEDULES

The study will consist of a screening visit, followed by visits at week 0, months 1,2, 3, and 4 and a final visit two weeks after discontinuation of Cycloset.

7.2 DESCRIPTION OF STUDY DAYS

7.2.1 Screening - Visit 0

Screening of subjects will occur at Visit 0.

- Consent form will be signed
- · Each subject will be assigned a study subject number
- Assessment of inclusion/exclusion criteria will be performed
- Medical history, including demographic and background assessments will be documented in the CRF
- Routine physical examination will be performed
- ECG test will be performed
- Blood will be taken for the determination of HbA1c, FPG, lipids, clinical chemistry variables (and serum pregnancy test for women of child-bearing potential); and hematology (see study schedule). Total amount of blood drawn at this visit will be approximately 20 ml.

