7.2.2.6 Call 3 (day 21)

- Study site will contact the subject by telephone to remind them to increase the dose of Cycloset to 4 tablets and assess tolerance. Subjects will be instructed to contact the study site if they experience intolerable nausea or vomiting.
- If at any time a subject is not able tolerate the next higher dose of Cycloset, they may stay at the current dose, providing it is at least 3 tablets per day.
- Assessment for any AE/SAE will be completed
- Subjects will schedule an appointment for the 1 month follow up visit on day 28 ± 3 days

7.2.2.7 *Visit 4 (Month 1)* \pm 3 days

- Assessment for any AE/SAE will be completed
- Medical history and weight will be taken
- Postural blood pressure measurements will be obtained first with the subject lying down and then repeated after 5 minutes of standing.
- Blood will be drawn for FPG and A1c. Total amount of blood drawn at this visit will approximately 10 ml.
- Subject will be reminded to increase the dose of Cycloset to 4 tablets if appropriate

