10 STATISTICAL PROCEDURES

10.1 ANALYSIS VARIABLES

A statistical analysis plan (SAP), providing details of the analyses and presentation structure of the results, will be developed and finalized before the database is locked.

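### The HbA1c that qualifies a subject is also the only one scheduled before treatment, so the single-arm change from baseline probably includes some regression to the mean

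*Combined protocol and SAP*

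**What the plan says.** Section 7.2.1 (Visit 0) provides that "Blood will be taken for the determination of HbA1c, FPG, lipids, clinical chemistry variables". Inclusion criterion 3 in section 4.2 sets the entry window, "HbA1c = 7.5-10.0" percent. Criterion 5 requires a stable GLP-1 analogue dose "for at least 90 days prior to determination of baseline A1C and eligibility for enrollment in the study protocol", which mentions the baseline value and eligibility together.

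In the study schedule, the HbA1c row is marked at Visit 0 and then at Visits 4 to 8. The visit descriptions agree:

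- Visit 1 lists aortic compliance only.
- Visit 2 includes an eligibility check ("Study entry criteria will be reviewed") and the meal test, but no HbA1c.
- Visit 3, the day of the first dose, has a blood draw: "Bloods for inflammatory markers and white blood cell isolation". HbA1c is not among the assays.
- Visit 4 (Month 1, on treatment) is where HbA1c next appears: "Blood will be drawn for FPG and A1c".

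Section 7.3.1 makes change from baseline in HbA1c a primary efficacy variable, alongside change in postprandial glucose metabolism. Section 5.1 states that "All subjects will receive Cycloset", so there is one arm, and section 5.4 says there is no run-in. Section 10.1 leaves the analysis to a SAP that "will be developed and finalized before the database is locked". Section 10.3 plans on a baseline of 8.0 ± 0.5%, a 0.6-point fall and 15 subjects.

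**The concern.** A single HbA1c is the subject's usual level plus a short-term deviation. Admitting subjects because that one value exceeds a floor over-represents those whose deviation happened to be upward. A later value will on average be lower with no treatment effect at all. A ceiling works the other way. With a planned mean much closer to the floor than to the ceiling, the floor probably dominates.

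In a controlled trial this drift affects both arms and cancels. Here nothing cancels it, and the analysis cannot separate it from drug effect. A later SAP can choose among the values collected, but it cannot supply a pre-dose sample that was never drawn.

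The qualifying value is also not recent at the first dose. Visit 0 is 1 to 3 weeks before Visit 1, Visit 2 is 7 to 10 days after Visit 1, and Visit 3 is 3 to 5 days after Visit 2. The gap is 7 + 7 + 3 = 17 days to 21 + 10 + 5 = 36 days, or 14 to 39 with the ±3 days allowed on Visit 1. The documents give no basis for quantifying what this adds.

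The meal-test co-primary is not affected in this way. Its baseline is measured at Visit 2 and is not the selecting measurement.

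**Working it through.** **The plan's own figure.** Fifteen subjects reproduce from the two-sided normal formula with doubled variance:

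n = 2 × (1.960 + 1.282)² × 0.5² / 0.6² = 14.6, rounded up to 15.

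This equals a paired calculation with an SD of change of 0.5 × √2 = 0.707. With an SD of change of 0.5, the paired normal formula gives 7.3, so 8. Section 10.3 does not say which SD the 0.5 is, nor the test or its sidedness. Both SDs of change are therefore carried below. Regression to the mean does not enter this formula.

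**Inputs for the bias.** From the documents: window 7.5 to 10.0, planned baseline 8.0 ± 0.5, n = 15. Not in the documents, so assumed: screened mean μ of 7.0, 7.25, 7.5, 7.75 or 8.0; between-person SD sb of 0.5, 0.6, 0.8 or 1.0; within-person SD sw of 0.2 or 0.3. That makes 5 × 4 × 2 = 40 combinations. The screened population is taken as normal, and the Month 4 deviation as unrelated to the Visit 0 deviation.

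**Formula.** With so² = sb² + sw², α = (7.5 − μ)/so and β = (10.0 − μ)/so:

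- admitted mean m = μ + so × [φ(α) − φ(β)] / [Φ(β) − Φ(α)]
- expected fall with no drug effect = (sw²/so²) × (m − μ)

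**Two worked cases.**

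- μ = 7.0, sb = 0.8, sw = 0.3: so² = 0.64 + 0.09 = 0.73, m = 8.03, bias = (0.09/0.73) × 1.027 = 0.127.
- μ = 8.0, sb = 0.5, sw = 0.3: so² = 0.25 + 0.09 = 0.34, m = 8.20, bias = (0.09/0.34) × 0.1995 = 0.053.

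| μ | sb | Bias, sw 0.2 / 0.3 | Admitted mean | Admitted SD |
|---|---|---|---|---|
| 7.0 | 0.8 | 0.059 / 0.127 | 8.00 / 8.03 | 0.41 / 0.43 |
| 7.5 | 0.8 | 0.038 / 0.083 | 8.15 / 8.17 | 0.49 / 0.50 |
| 8.0 | 0.5 | 0.023 / 0.053 | 8.17 / 8.20 | 0.42 / 0.45 |
| 8.0 | 0.6 | 0.023 / 0.052 | 8.23 / 8.26 | 0.47 / 0.49 |

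**Which cases fit the plan.** Requiring an admitted mean within 0.3 of 8.0 and an admitted SD within 0.1 of 0.5 leaves 21 of the 40. Their bias runs from 0.023 to 0.127, median 0.053. Against 0.6 that is 0.023/0.6 = 4% to 0.127/0.6 = 21%. Over all 40 the range is 0.017 to 0.218, but the four above 0.127 have an admitted SD of 0.27 to 0.36, below the planned 0.5. At a screened mean of 8.75, the window midpoint, the bias is zero. Above that it reverses slightly.

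**Effect on the test.** Two-sided one-sample t at 5%, n = 15, no drug effect:

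| Bias | Rejection rate, SD of change 0.5 | SD of change 0.7 |
|---|---|---|
| 0.02 | 5.2% | 5.1% |
| 0.05 | 6.5% | 5.8% |
| 0.08 | 8.9% | 7.0% |
| 0.13 | 15.6% | 10.3% |

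**What a Visit 3 baseline would do.** If r is the correlation between the Visit 0 and Visit 3 deviations, a share r of the bias remains. For r of 0.3 to 0.7, 0.038 to 0.089 remains of 0.127, and 0.016 to 0.037 of 0.053. If deviations persist to Month 4 with correlation 0.1 to 0.3, the unfixed 0.127 is itself only 0.9 × 0.127 = 0.114 to 0.7 × 0.127 = 0.089. The amount removed, (1 − r) × 0.127, is unchanged.

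**The case against.** The strongest reply is that the bias is small beside the trial's own imprecision. With 15 subjects the standard error of the mean change is 0.5/√15 = 0.129 to 0.707/√15 = 0.183, so every fitting case lies below one standard error. At the median of 0.053 the false-positive rate is about 6% to 7%. With r = 0.5 the fix then removes only about 0.026 points.

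The range itself is soft at both ends. Every fitting value above 0.06 needs an assumed within-person SD of 0.3. The 0.127 case also needs 72% of screened subjects to fall outside the HbA1c window. At the low end, a screened mean of 8.1 with sb 0.5 to 0.6 and sw 0.2 also fits and gives 0.018 to 0.019, and a within-person SD of 0.15 gives about 0.01. The 15.6% rejection rate goes with an SD of change of 0.5, which does not reproduce 15 subjects. The SD of about 0.7 does, and it gives about 10%.

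Criterion 5 sets the clock for stable GLP-1 dosing and is not a definition of the analysis baseline. The missing control arm limits attribution far more, and the open-label single-cohort design is openly stated.

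All of this stands as a limit on size and emphasis. It does not answer the point. The inference about baseline rests mainly on the schedule, which offers no other pre-dose HbA1c. The error is systematic, affects a co-primary estimate, and can be reduced by a fresh sample only before dosing.

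**Conclusion.** The concern holds and should be fixed. The missing pre-dose sample and the mechanism are certain from the documents. The direction is probable, because the planned baseline sits near the entry floor. The size is not established. Under the assumptions above it is about 0.02 to 0.13 HbA1c points, centred near 0.05, and it could be about 0.01 under other assumptions that also fit. It would overstate the effect somewhat and would not explain most of a 0.6-point fall. These figures rest on an assumed screened distribution and within-person SD, normality, and an independent Month 4 deviation.

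**What to change.** - Add one HbA1c to the blood already drawn at Visit 3, before the first dose, and mark it in the schedule.
- Define that value as the baseline for the HbA1c endpoint, in section 7.3.1 and in the SAP.
- Use the Visit 0 value for eligibility only, and state that the HbA1c entry window is not re-applied to the Visit 3 value. Visit 3 follows the entry review at Visit 2, so the new value need not enter eligibility. Re-applying the window would bring the selection back.
- Reword criterion 5 so that the eligibility value and the baseline value are distinct.
- Keep the change from Visit 0 as a sensitivity analysis.

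The cost is about 15 assays, plus one per replaced subject, with no added visit, procedure or staff. The protocol already measures HbA1c at both Visit 7 and Visit 8, 3 to 5 days apart, so one dedicated baseline assay is proportionate. The observed mean change may come out slightly smaller. The fix removes a share 1 − r of the bias and leaves the lack of a control arm as it is, which the report should state as a limitation.
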